NIR Stimulation for Alzheimer’s disease. To date, there have been **no published RCTs on the efficacy of NIR-PBM stimulation in those at risk for Alzheimer’s disease**. A study by Saltmarche et al. (2017) was limited to a **case series of 5 individuals with probable AD** receiving transcranial and intranasal NIR-PBM over 12 weeks of active treatment, followed by a 4-week withdrawal period. Immediate post-testing after 12-weeks of intervention revealed significantly higher scores on the Mini-Mental State Exam and Alzheimer’s Disease Assessment Scale (ADAS-Cog), as well as improved functional behaviors. With discontinuation of NIR-PBM, all participants showed significant decline. In a second study, **independently living older adults** (N=12, ages 49-90 yrs) received weekly stimulation (1064 nm, laser, 8 minutes duration) for 5 weeks (Vargas et al., 2017). Findings were significant for pre-post intervention changes in reaction time, memory, and resting state EEG, and a more efficient fMRI response over the frontal brain region. Critically, **neither study with older adults included a sham control group**.

Pilot Data from UF. We recently completed a small well-controlled proof of concept pilot study to determine whether NIR-PBM might benefit cognition and neuroimaging. Our pilot was randomized, double-blinded, sham controlled and designed to derive effect sizes. It involved transcranial (116 MedX Console) and intranasal (Vielight Inc.) delivery of active or sham NIR light using methods described by Naeser et al. (2014) Participants completing this initial pilot study included 13 healthy community residing older adults in their mid-70’s who were randomized to Active (N=8) or Sham groups (n=5). The intervention involved six 40-minute sessions, given 3 times a week over a 2-week period. The Active and Sham conditions were identical with the exception that no actual NIR light was delivered during Sham. For both conditions, six transcranial superluminous clusters were placed on the scalp, *following the 10-20 EEG system*, targeting bilateral frontal, temporal, parietal and central sites. Intranasal diodes were used to target inferior frontal and limbic regions. Cognitive/behavioral outcomes were obtained before and immediately after intervention.

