Aim 1: To evaluate whether NIR-PBM stimulation can improve cognitive function in older adults with increased risk for Alzheimer's disease. Specifically, we plan to test whether 12 weeks of NIR stimulation, relative to sham, improves performance on memory (primary outcome) and executive function tasks sensitive to hippocampal and frontal brain function in older adults with increased risk for Alzheimer's disease. We hypothesize that NIR stimulation will result in greater improvement on tasks of H1.1) episodic memory and H1.2) executive function relative to sham. The primary outcome measure will be a spatial navigation task (ARENA), a human analogue to the Morris Water Maze¹⁷, that is sensitive to hippocampal function. A secondary cognitive outcome measure will be the executive function working memory composite score from the NIH Examiner battery known to be sensitive to frontal brain function.

Aim 2: To evaluate whether NIR-PBM intervention enhances brain function and connectivity in those at increased risk for Alzheimer's disease. We plan to test whether 12 weeks of NIR stimulation leads to enhanced markers of 31-P MRS ATP and rs-fMRI functional connectivity in older adults with increased risk for Alzheimer's disease. We hypothesize that: H2.1) NIR stimulation will produce pre-post increases in frontal and medial temporal brain markers of MRS ATP function and

H2.2) pre-post increases in functional connectivity in frontal and medial temporal lobe mediated resting state brain networks.

Exploratory Aim: To examine how baseline demographic, mood, vascular risk, genetic, and neuroimaging factors influence individual differences in cognitive outcome for NIR-PBM intervention. We plan to evaluate how baseline MRI white matter abnormalities, apolipoprotein E (APOE) ε4 status, and metabolic/vascular risk factors of hypertension and diabetes influence cognitive outcomes after 12 weeks of NIR stimulation. Additional factors include demographic (age, education, gender), mood status, and general processing efficiency. For this exploratory aim, we hypothesize that: HE.1) greater white matter lesion load on FLAIR MRI, HE.2) metabolic-vascular risk factors of hypertension and diabetes, and HE.3) APOE ε4 status will each predict poorer NIR-PBM outcomes in memory and executive function.

[figure not shown]
7. Research Plan

7.1 Design Overview.

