7.5.1 Cognitive Outcome Measures (Aim 1)

[figure not shown]
The cognitive outcome measures are described in more detail below and include the **primary outcome (ARENA)** and various experimental and clinical exploratory measures. An additional subset of cognitive measures is optional and depends on available time. These optional measures will allow comparison with an ongoing study that is IRB-approved.

7.5.1a. Primary Outcome – ARENA: This is a task of spatial memory and navigation that has been linked to hippocampal function and is a human analogue to the Morris water maze used in animal studies. At UF, this task has been used in other IRB-approved studies with older adults (the VITAL study), those with Essential tremor, those with mild cognitive impairment and Alzheimer's disease. We selected **ARENA** (Thomas et al., 2001) as our **primary cognitive outcome** for the following reasons: a) the large effect size noted in our pilot NIR study; b) its sensitivity to hippocampal neuronal loss and early amnestic MCI (Laczo et al., 2010, 2011, 2012; Hort et al., 2007; Gazova et al.m 2012); and c) observations that the animal version (Morris Water Maze) benefitted from NIR stimulation in a transgenic mouse model (DeTaboada et al., 2011).

The task is given on a computer and participants are trained in the use of a joystick before beginning the task. Participants must navigate in a virtual, 3-D room displayed on a computer screen and find an invisible target on the floor as quickly and efficiently as possible. Shown below are sample walls of the virtual room. The participant uses a joystick to navigate this “arena”, which is designed to look like a pool of water (the blue on the pictures). The arena is bordered by a low wall and is in its entirety located in a perfectly square room, with each of the four walls of the room differentiated from the others by 1-2 unique, fractal-based patterns.

Practice and Visible Target Trials. The task begins with a 5-10 minute orientation session, in which they practice using the joystick and then navigate to visible targets on the floor. In the figure to right, the white elliptical circle represents the target. Performance on up to 5 visible-target navigation trials ends the practice session. The recorded path length and time to acquire the target serves as a baseline against which invisible target trials will be evaluated.

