Hidden target condition. Practice trials are followed by 8 invisible-target learning trials. In these trials the target is not visible from afar and is discoverable only when the joystick hovers over the target. A trial begins with a fixed tour of a new room, where each wall is shown for approximately 2 seconds during two sweeps of the room. Participants are instructed that the hidden target will be in the same place on each trial and that their task is to find it as soon as possible. Participants are typically given 120 seconds to find the target. During the first 2 trials, the examiner takes over after 120 seconds and assists the participant finding the target. No assistance is given after the initial two trials. If the target has not been located after 120 seconds in the later trials, the trial ends and a 10-second inter-trial interval (ITI) ensues, and the next trial begins. If the subject acquires the target on any trial, it becomes visible and a pleasant auditory signal additionally alerts them to target acquisition. They are allowed to stay on the acquired target for 15 seconds and are encouraged to rotate-in-place to survey the environment. After this, the 10-second ITI ensues and the next trial begins at a different compass point.

A final spatial memory probe occurs during the 9th and final trial. On this final trial, the invisible target is removed unbeknownst to the participant. This means that target acquisition is not possible, but search behavior is evaluated with regard to the percent of the 120-second trial that is spent in the quadrant containing the target. On each acquisition trial, path length, time to acquire the target, and target acquisition (yes-no) are recorded. On the probe trial, path length and percent of time spent in each quadrant of the Arena are recorded. The **primary outcome variable** is a **composite score**, consisting of mean z-scores on path length, time to acquire target, and percent of time spent in the proximal quadrant on the probe trial (Trial 9). Additional variables are also computed.

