7.5.3c Processing Speed: Processing speed, a potential contributor or mediator of both memory and executive function, will be assessed using reaction time subtests from the **California Computerized Assessment Package (CALCAP-RT; Miller, 2013)**. The **CALCAP** is a comprehensive tool for assessing reaction time, speed of information processing, rapid visual scanning, form discrimination, brief memory and divided attention. We plan on administering the **abbreviated version**, which consists of 4 subtests that take approximately 8-10 minutes. All tasks are given on a computer. The 4 subtests are described below.

- Simple Reaction Time. Subjects are asked to press a key as soon as they see anything at all on the screen. This procedure provides a basal measure of reaction time.
- Choice Reaction Time for Single Digits. Subjects are asked to press a key as soon as they see a specific number such as '7', otherwise they are to do nothing. This procedure adds a simple element of memory to the task.
- Serial Pattern Matching 1 (Sequential Reaction Time 1). Subjects are asked to press a key only when they see two of the same number in sequence, for example, if they see the number '3' followed by a second occurrence of the number '3'. This procedure adds a more complex element of memory since the subject must keep in mind the last number that was seen.
- Serial Pattern Matching 2 (Sequential Reaction Time 2). Subjects are asked to press a key only when they see two numbers in sequence (increasing order). For example, if they see the number '3' followed by the number '4', the number '6' followed by '7' and so on.

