Title: Revitalizing Cognition in Older Adults at Risk for Alzheimer's Disease
using Near Infrared Photobiomodulation

[figure not shown]
8-1-2025

NCT04018092

STATISTICAL DESIGN AND POWER

Sample Size Determination/Power Analysis

The sample size calculation was based on our pilot results of all primary and secondary measures in Aim 1 and Aim 2. Here we use ARENA, our primary outcome that is being tested in Aim 1 (see H1.1) to illustrate the power calculation procedure. From our pilot data, the mean difference of ARENA score changes between active stimulation group ($n = 8$) and sham ($n = 5$) group was 0.58. Based on a pooled standard deviation of 0.55, the standardized effect size (Cohen's d) is $d=1.06$. Similarly, we calculated the standardized effect sizes of our secondary outcome variables, including working memory (H1.2, $d=0.67$); prefrontal cortex ATP (H2.1, $d=0.48$); temporal lobe ATP (H2.1, $d=0.5$); prefrontal cortex connectivity (H2.2, $d=1.3$); and temporal lobe connectivity (H2.2, $d=1.1$). Based on our experience of 10% attrition in a clinical trial with three months of intervention for the ACT study (MPI: [name]; PI UA Field Site: [name]) that is currently underway at the UF and UA field sites, we conservatively assumed 15% attrition in the power calculations for the current proposal. At 5% alpha level and assuming the 15% attrition rate, the power trajectories for different measures with respect to number of samples per treatment group are shown in the above figure. In order to guarantee that all these primary and secondary measures have more than 80% power, we plan to enroll a total of 168 participants (84 per group, shown as the dashed line in the above figure). This large sample size will also ensure sufficient statistical power for the exploratory analysis of Aim 3, where we will examine potential mediators and moderators in relation to the intervention response. Note that we are powering the study based on a 2-week session and the actual effect sizes (from a 12-week NIR stimulation session) will likely exceed these minimal estimates.

Statistical Analysis

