stimulation group, β is the post intervention treatment effect (active stimulation effect compare to sham group) and $\mathbb{I}(\cdot)$ is the indicator function which equals to 1 if the argument inside (\cdot) is true and equals 0 otherwise; x_{il} is the l^{th} covariates for subject i with $l = 0$ for baseline level (e.g. baseline ARENA for Aim 1) and $l = 1, 2, \dots, L$ for L covariates (i.e., age, sex, education...); η is the time effect of 3-month follow-up compared to post-intervention visit; θ is the interaction effect between follow-up and active stimulation; $\varepsilon_{ik} \sim N(0, \sigma^2)$ is the error term with variance σ^2 . In equation (1), β is the active stimulation effect for post-intervention, and we will perform the statistical hypothesis testing ($H_0: \beta = 0$) to provide its p-value, point estimate and confidence interval. Similarly, $\beta + \theta$ is the active stimulation effect after 3-month follow-up, where p-value, point estimate and confidence interval will be similarly obtained by testing the null hypothesis $H_0: \beta + \theta = 0$. Note that equation (1) will be applied to all measures in Aim 1 including the primary outcome (ARENA), secondary outcomes (working memory), and other exploratory outcomes (verbal fluency, mnemonic similarity, auditory verbal learning test, and Stroop color word test).

Analyses for Aim 2: To test the hypothesis that NIR stimulation will result in greater pre-post intervention improvement in neuroimaging (31P MRS for ATP and rs-fMRI for connectivity) relative to the sham group, we will fit the following linear mixed model:

$$y_{ik} = \mu + \alpha_i + \beta \mathbb{I}(z_i = 1) + \sum_{l=0}^L \gamma_l x_{il} + \varepsilon_{ik}, \alpha_i \sim N(0, \sigma_0^2), \varepsilon_{ik} \sim N(0, \sigma^2) \quad (2)$$

Equation (2) is similar to equation (1), with the adjustment of the same set of covariates, except that the equation (2) doesn't have the 3-month follow-up. β is the active stimulation effect for post-intervention, for which we will perform the statistical hypothesis testing ($H_0: \beta = 0$) to provide its p-value, point estimate and confidence interval. Note that equation (2) will be applied to all measures in Aim 2 including secondary outcomes involving ATP from 31P MRS (H2.1) and connectivity from, rs-fMRI (H2.2).

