Analysis for Exploratory Aim 3: We want to further explore whether APOE $\varepsilon 4$ carrier status, vascular comorbidities, Fitzpatrick skin type questionnaires, processing speed, and mood are potentially confounders, moderators, or mediators. To examine confounders, we will directly adjust these variables as covariates in the linear mixed model in equation (1) and equation (2). A statistically significant covariate effect will imply the potential confounding roles of these variables. To examine moderators, we will include these variables and their interactions with the intervention effect (one variable at one time) in equation (1) and equation (2). A statistically significant interaction effect will imply the variable can be a moderator. To examine mediators, we will perform mediation analysis¹⁶¹⁻¹⁶². The mediation effects of these variables and their 95% confidence interval will be determined using the R *mediation* package¹⁶³.

For each of the specific aims listed above, we will further conduct exploratory analysis stratifying by sex, to examine its relevant biological effect. In other words, we will disaggregate the data by sex and evaluate the active stimulation effects for male and female, respectively.

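### Does the protocol leave open whether the primary ARENA score is corrected for visible-target performance, so that a speed gain could pass for memory?

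*Protocol*

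**What the plan says.** Protocol section 7.5.1a describes ARENA in two stages. In the practice stage, participants steer to visible targets on up to five trials. Of those trials the protocol says: "The recorded path length and time to acquire the target serves as a baseline against which invisible target trials will be evaluated". In the hidden-target stage there are eight learning trials, typically capped at 120 seconds, and a ninth probe trial. The primary outcome variable is then named as a composite "consisting of mean z-scores on path length, time to acquire target, and percent of time spent in the proximal quadrant on the probe trial", followed by a remark that further variables are also computed.

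The hypothesis is worded in terms of memory (Protocol section 6, Aim 1): "We hypothesize that NIR stimulation will result in greater improvement on tasks of H1.1) episodic memory and H1.2) executive function relative to sham".

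The SAP takes the ARENA score as the outcome in equation (1) without listing its components. Its baseline term is the pre-intervention visit, "for baseline level (e.g. baseline ARENA for Aim 1"), not visible-target performance. The SAP's Statistical Analysis section also adjusts for age, sex, education and the potential confounders listed under Aim 3. That list asks whether "processing speed, and mood are potentially confounders, moderators, or mediators", so processing speed is on it.

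**The concern.** The two sentences in section 7.5.1a can be read as two scoring rules for one endpoint: raw path length and time, or path length and time judged against the same person's visible-target performance. The SAP does not say which.

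The difference could matter for interpretation. Time to target depends partly on how fast someone moves the joystick. The Background reports a study of older adults treated with NIR light: "Findings were significant for pre-post intervention changes in reaction time, memory, and resting state EEG". Section 7.5.3c calls processing speed "Processing speed, a potential contributor or mediator of both memory and executive function". If active treatment made people faster without improving memory, the gain would appear in one arm only and would not cancel in the treatment coefficient. Adjusting for pre-intervention ARENA removes differences that existed before treatment, not a change caused by it. An uncorrected composite could then credit a speed effect to episodic memory. If the scoring were chosen after the results were seen, the type I error would also rise.

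**Working it through.** **1. The two statements side by side.** The practice-trial sentence says what visible-target values are compared with. It gives no difference, ratio or covariate form, and mentions neither the composite nor the primary outcome. The hidden-target paragraph names the primary variable and lists its three parts. On an ordinary reading the specific definition governs, and the visible-target comparison is among the additional variables. It is also possible that path length and time are visible-adjusted before z-scoring, so some ambiguity remains, but the text does not set out two rival primary rules.

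**2. The plan's own figures.** From the SAP's power section, the pilot mean difference is 0.58 ("Based on a pooled standard deviation of 0.55, the standardized effect size" follows). So d = 0.58 / 0.55 = 1.05 against the stated 1.06; rounding of the inputs allows 1.04 to 1.07. With 84 per arm and 15% attrition, 84 × 0.85 = 71.4, or 71 per arm. The sample size is driven by the smallest planning effect, d = 0.48: 70 per arm by t test, and 70 / 0.85 rounds up to 83, against the planned 84. None of this depends on how ARENA is scored.

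**3. Size of a speed-only effect on the composite as defined.** Assumptions: equal weights (a mean of three z-scores), signs aligned so that higher is better, only the time item moved by v SD, composite SD 0.55, 71 per arm, two-sided 5% t test. The documents give no v, so a range is shown.

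Shift = v / 3; d = shift / 0.55.

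| v (SD of time) | composite shift | d | chance of p < 0.05 |
|---|---|---|---|
| 0.2 | 0.07 | 0.12 | 11% |
| 0.3 | 0.10 | 0.18 | 19% |
| 0.5 | 0.17 | 0.30 | 43% |

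An 80% chance needs a composite shift of 0.55 × (1.96 + 0.84) × √(2/71) = 0.26, so a time shift of 3 × 0.26 = 0.78 SD. Reproducing the whole pilot difference by speed alone would need 3 × 0.58 = 1.74 SD.

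The 0.55 is the SD of change in 13 people. If the SD is instead derived from an inter-item correlation r, it is √((3 + 6r)/9): 0.58 at r = 0 and 0.89 at r = 0.7. The chance at v = 0.5 is then 40% and 20%.

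**4. Why only the time item is moved.** Path length is distance. Moving faster along the same route leaves it unchanged, and on trials that hit the 120-second cap a faster navigator covers more ground, which worsens it. A shorter path means a more efficient search, which is largely what a spatial-memory task is meant to detect.

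**5. Whether a visible-target reference would remove the effect.** An illustrative simulation with assumed distributions made navigation 20% faster with memory unchanged, and let 2% to 24% of trials hit the cap.

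| Treatment of time | composite shift |
|---|---|
| none (composite as defined) | +0.05 to +0.10 |
| visible time subtracted | +0.03 to +0.07 |
| divided by visible time | −0.01 to −0.13 |

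The uncorrected shift corresponds to d of 0.09 to 0.18 (0.05 / 0.55 and 0.10 / 0.55), or about an 8% to 19% chance of p < 0.05. Subtraction leaves most of it, and division can overcorrect. The shift is exactly zero only if the gains on visible and hidden trials are equal in z units and the z-scores are subtracted.

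**The case for a change.** The strongest case for a change is that this is the trial's only primary outcome, the visible-target sentence is unconditional and sits in the primary-outcome section, and one paragraph would settle the matter with data already collected. The practice-trial sentence treats both path length and time as needing a reference. If better joystick control moved both items by 0.3 SD, the composite would shift by 2 × 0.3 / 3 = 0.20, d would be 0.36, and the chance of p < 0.05 would be 58%. If either scoring could be picked after seeing results, simulated type I error is about 8% instead of 5%. The planned processing-speed analysis uses a reaction-time battery, not joystick navigation, and its mediation part is exploratory.

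Some of this stands. The SAP does not define the score, a baseline covariate would not absorb a speed change caused by treatment, and a sentence of clarification would do no harm. The rest carries less weight. The two-item figure describes better steering or search, not pure speed. The 8% requires a choice made after seeing results, which nothing in the documents suggests. The reaction-time finding comes from 12 people without a sham group, and memory changed as well, so it is weak support for a speed-only gain confined to the active arm.

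**Conclusion.** This is missing detail that analysts can fill sensibly from the text. Protocol section 7.5.1a names one primary variable and gives its three parts. Scoring it that way yields a valid randomised comparison on the named outcome, with sample size and design untouched. Visible-target path length and time are already recorded, and comparing hidden trials with them is already foreseen, so the arm difference in visible-target performance can be shown beside the primary result to help interpret it.

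The exposure is modest: a composite shift of 0.07 to 0.17 for an assumed time shift of 0.2 to 0.5 SD, with an 11% to 43% chance of significance at 71 per arm and SD 0.55, and less with a larger SD. This rests on equal weights, aligned signs, a speed effect acting through time alone, and a v that the documents do not supply. Requiring a visible-target correction would bring no assured gain, since its effect ranges from leaving most of the shift to reversing its sign, depending on a form the documents do not give.
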